3.2 Primary Study Endpoints

The primary end point is the number of migraine days per month during treatment with metformin 500mg BID vs placebo for 12 weeks.

3.3 Secondary Study Endpoints

The secondary end point is the percentage of patients with >50% reduction in migraine days per month (response rate).

3.4 Primary Safety Endpoints

To determine the safety and tolerability of metformin in patients with migraine.

Hypothesis: Metformin treatment will be safe and well tolerated, with limited adverse effects.

4 Subject Selection Enrollment and Withdrawal

4.1 Inclusion Criteria

Inclusion criteria are as follows: 1) age 18-65 years, 2) a diagnosis of migraine with or without aura for >1 year according to the International Classification of Headache Disorders-IIIb (2013), and 3) 5-25 migraine days per month on average during the preceding 3 months. Women of reproductive ability must use a reliable form of contraception beginning 3 months before study enrollment, throughout the study, and for at least 1 month after study completion.

4.2 Exclusion Criteria

Exclusion criteria are as follows: 1) a diagnosis of diabetes mellitus or polycystic ovarian syndrome, 2) overuse of acute migraine treatments, 3) failure to respond to 3 or more previous preventive drug treatments, 4) change in dose of migraine-preventive medication within 2 months of beginning the baseline diary phase, 5) initiation of cranial nerve blocks within 2 months of beginning the baseline diary phase, 6) initiation of Botox within 12 months of beginning the baseline diary phase, 7) significant somatic or psychiatric disease, 8) known alcohol or other substance abuse, and 9) pregnant or breastfeeding.

4.3 Subject Recruitment, Enrollment and Screening

Subjects will be recruited from the outpatient Mayo Headache Clinic, Mayo Women's Health Clinic, Mayo Community Internal Medicine, and the Mayo Clinic- Arizona State University Neurology Clinic. The Headache Clinic employs 6 headache specialists and 1 fellow which is sufficient staffing to support this proposal and recruitment of patients with high-frequency migraine within 6 months.

4.4 Early Withdrawal of Subjects

4.4.1 When and How to Withdraw Subjects

Subjects may withdraw from the study prior to that subject completing all of the study related procedures for the following reasons:

- Subject safety issues
- Failure of subject to adhere to protocol requirements
- Subject decision to withdraw from the study (withdrawal of consent)

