3.1 General Design

We will obtain approval from the Mayo Clinic Institutional Review Board, and all patients will provide written, informed consent before study enrollment.

This will be a single-center, double-blind, randomized, placebo-controlled, crossover study.

After study enrollment, patients will be randomized to the Metformin study drug group or the placebo group. The Principal Investigator or patient can't choose the study group. The patient will have an equal chance of being assigned to the Metformin group. Neither the patient or the Principal Investigator will know which study group they are participating in. In case of an emergency, this information will be available.

Patients will undergo a 2-hour oral glucose tolerance test to confirm the absence of diabetes mellitus. Subjects will then keep a paper headache diary for 4 weeks to establish baseline characteristics, including number of migraine days per month, number of moderate to severe headache days per month, and number of days per month of acute medication use. The 4-week baseline period will be followed by 2 treatment periods of 12 weeks each, separated by a

washout period of 4 weeks (total study duration, 32 weeks). During the washout period, we will washout the study drug x 4 weeks.

For the 12-week treatment periods, subjects will receive either metformin 500mg twice daily or matching placebo twice daily. During the first week of each 12 week treatment period, patients will receive metformin 250mg twice a day or matching placebo. At week 2, the dose will be increased to metformin 500mg twice a day or matching placebo. In case of intolerable side effects, the dose will be reduced to 250mg twice a day.

Subjects will have 7 clinic visits. Routine laboratory studies and a pregnancy test will be performed at enrollment and week 20. Abnormal kidney or liver function will exclude subjects. Pregnancy will exclude subjects. General and neurologic examinations will be performed during 2 of the 7 visits. At each visit, subjects will receive medication for the period until the next visit. A paper headache diary will be used for the trial. For every day that the subject has a headache of any type, she or he will record headache characteristics, associated features, and medications used.

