4.4.2 Data Collection and Follow-up for Withdrawn Subjects

Even though a subject has withdrawn from the study, it may be important to collect some follow-up or survival data on such subjects throughout the protocol defined follow-up period. Such data is important to the integrity of the final study analysis since early withdrawal could be related to the safety profile of the study drug. If a subject withdraws consent to participate in the study, for subject safety reasons, we will make every effort to obtain permission to collect follow up information.

5 Study Drug

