5.8 Masking/Blinding of Study

Patients will be allocated to the metformin-placebo sequence or the placebo-metformin sequence at random in a 1:1 ratio. The statistician will create the randomized treatment allocation schedule by using a computer random number generator. The randomized treatment allocation schedule will be concealed by storing it on the REDCap Randomization Module. The Mayo Clinic Pharmacy will allocate patients to treatments using the REDCap Randomization Module.

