7.1 Sample Size Determination

This will be a single-center, double-blind, randomized, placebo-controlled, crossover study. Crossover designs have been used successfully in migraine trials (Olesen, 1981). Prior migraine trials have suggested that a sample size of 34 patients has 80% power to detect a mean reduction in migraine days of 1.25 days per month, with $\alpha=0.05[Q^1]$ (σ 2.5, ρ 0.5; Hauge, 2009; Silberstein, 2004; Sorensen, 1986). We will enroll 40 subjects to account for an estimated 15% dropout rate.

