7.2 Statistical Methods

The primary end point is the number of migraine days per month during treatment with metformin vs placebo. The secondary end point is the percentage of patients with >50% reduction in migraine days per month (response rate). Mean 4-week migraine frequency for patients receiving metformin vs placebo treatment will be assessed by using the Hills-Armitage method. Response rate will be assessed by using the McNemar test. The frequency of adverse events during metformin treatment will be compared to that during placebo treatment by using the McNemar test.

Descriptive Statistics

Univariate descriptive statistics and frequency distributions will be calculated, as appropriate for all variables.

Handling of Missing Data

Patients will be included in the primary analysis on the basis of intention to treat. Migraine frequency will be calculated using all available follow-up data and converted to units of frequency per four weeks.

Multiplicity

There is a single primary outcome measure. If the primary analysis is statistically significant, the secondary outcome measure will be assessed in order to facilitate interpretation of clinical importance.

Interim Analysis

There will be no interim analysis for early stopping due to efficacy.

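### Subjects can leave the study for nonadherence, and possibly on week-20 tests, with no duty to continue the headache diary, so the declared intention-to-treat analysis can become a selected subset

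*Combined protocol and SAP*

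**What the plan says.** **Leaving the study.** Section 4.4.1 gives three reasons for leaving before all study procedures are complete: safety, the subject's own decision, and "Failure of subject to adhere to protocol requirements". The section does not distinguish stopping study drug from ending participation. Section 5.5 says compliance will be monitored but sets no threshold.

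**Week 20.** Sections 3.1 and 6 schedule laboratory work and a pregnancy test at enrollment and again at week 20. Both then say "Abnormal kidney or liver function will exclude subjects", with a parallel sentence for pregnancy. Neither says whether this applies at both times, or whether the drug, the diary or both would stop. The visit list in section 3.1 links tests to eligibility only at the screening visit. At week 20 it lists the tests and a new drug supply, with no exclusion step.

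**Follow-up after withdrawal.** Section 4.4.2 says "it may be important to collect some follow-up or survival data on such subjects". It adds that such data matter to the final analysis because withdrawal may be linked to drug safety. The diary is not named and nothing is required.

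**Analysis.** Section 7.2 says "Patients will be included in the primary analysis on the basis of intention to treat". It uses whatever diary data exist, rescaled to a four-week rate. The primary comparison is by Hills-Armitage; response rate and adverse events are compared by McNemar. Section 7.3 includes every randomized subject who took at least one dose. There is no rule for a subject with data from one period only, and no sensitivity analysis for missing data.

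**The concern.** An intention-to-treat analysis needs outcome data from subjects who stop or misuse the drug as well as from those who take it as planned. Here the diary is the only source of the primary outcome, and the plan allows it to end when a subject leaves for nonadherence.

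Such losses may depend on treatment. Nonadherence can follow from side effects or lack of benefit. Section 5.6 bars overuse of acute medication, so a subject doing badly in one period could breach a protocol requirement for that very reason. A laboratory finding at week 20 comes just after period 1, so removal at that point could differ between the two sequences.

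The crossover makes the loss more costly. Hills-Armitage works on the difference between a subject's two periods, and McNemar on pairs. A subject with no data in one period therefore adds nothing to the treatment contrast, even if the other period is complete. What remains at stake is whether the reported effect describes all treated subjects or only those who reached period 2.

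**Working it through.** **1. Inputs from section 7.1.** "sample size of 34 patients has 80% power to detect a mean reduction in migraine days of 1.25 days per month"; "σ 2.5, ρ 0.5"; alpha 0.05 (sidedness is not stated; two-sided is assumed here and reproduces the figure); "We will enroll 40 subjects to account for an estimated 15% dropout rate".

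**2. The plan's own figures.**
- SD of the within-patient difference: 2.5 × √(2 × (1 − 0.5)) = 2.5.
- Normal approximation: n = (2.5 × (1.960 + 0.842) / 1.25)² = 31.4, rounded up to 32.
- Noncentral t at n = 34: power 80.8% on 33 degrees of freedom (paired t), or 80.7% on 32 (two sequences, as in Hills-Armitage).
- Enrollment: 34 / 0.85 = 40.

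The 34 and the 40 both reproduce.

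**3. Who is lost from the contrast.**

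| When the subject leaves and the diary stops | Period 1 rate | Period 2 rate | Within-patient difference |
|---|---|---|---|
| During period 1 | yes, rescaled | none | none |
| During washout or at week 20 | yes | none | none |
| Part-way through period 2 | yes | yes, rescaled | usable |

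The rescaling rule in section 7.2 recovers the third row. It cannot supply a period that has no data, so the first two rows stay out of the comparison.

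**4. Illustrative bias.** Let f be the share with no pair, 1.25 days the effect in completers, and e the effect in those lost. The values of e are assumptions; the documents give none. The effect over all subjects is (1 − f) × 1.25 + f × e, while the paired analysis estimates 1.25.

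| f | e | Effect over all subjects | Overstatement |
|---|---|---|---|
| 15% | 0.625 | 0.85 × 1.25 + 0.15 × 0.625 = 1.156 | 0.094 days; 1.25/1.156 = 1.08 |
| 15% | 0 | 0.85 × 1.25 = 1.0625 | 0.1875 days; 1.25/1.0625 = 1.18 |
| 25% | 0.625 | 0.75 × 1.25 + 0.25 × 0.625 = 1.094 | 0.156 days |
| 25% | 0 | 0.75 × 1.25 = 0.9375 | 0.3125 days |

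**5. Power by number of complete pairs** (effect and SD unchanged, degrees of freedom n − 2): 40 pairs 86.9%; 36 pairs 83.0%; 34 pairs 80.7%; 32 pairs 78.1%; 30 pairs 75.3%; 28 pairs 72.1%. At the planned 15% loss, power is as stated. It falls below 80% only if more than 15% lack a pair.

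**The case against.** The strongest reply is that the plan already guards against much of this. Section 4.4.1 is permissive and no adherence threshold triggers removal. Section 7.3 keeps everyone who took a dose. Sections 3.1 and 6 let subjects with intolerable side effects continue at a reduced dose, so poor tolerance does not by itself end participation. Section 4.4.2 acknowledges that data after withdrawal matter. These points stand, and they limit what can be claimed.

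Several stronger readings are tempting, but the documents do not support them:

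- *The analysis will be an adherent subset.* This is a risk and not a certain result. Adherence also describes only one route; week-20 exclusions would select on laboratory findings or pregnancy.
- *Anyone who leaves in period 2 is lost.* The rescaling rule keeps those with some period-2 diary days.
- *Exclusion at week 20 is a stated rule.* It is one fair reading of sections 3.1 and 6, and the visit list shows no such step. The text is ambiguous.
- *The effect will be overstated by 18%.* That is the upper end of the range at 15% loss. It assigns the whole dropout allowance to subjects without a pair and sets their effect to zero. Some dropout will be withdrawal of consent, which no diary rule recovers. Zero effect is also doubtful for week-20 exclusions: metformin-first subjects may already have had 12 weeks of drug, and findings in placebo-first subjects cannot be due to it.
- *The sample size is wrong.* The 15% loss is already built in.
- *The nonadherence clause should be deleted.* Protocol requirements also cover matters such as contraception and acute-medication overuse, so deletion would reach into subject management.

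What none of this answers is that no sentence requires the diary after withdrawal and no rule covers one-period subjects.

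**Conclusion.** The concern holds in a limited form. A stated reason for leaving the study, an unclear exclusion at week 20 and a non-binding follow-up clause together leave the intention-to-treat label without the data collection it needs. Following the plan as written can lose a whole period of primary-outcome data for reasons that may be related to treatment.

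The size cannot be determined from the documents. The 8% to 18% range rests on three assumptions: the full 15% lack a pair, completers have the planned effect, and those lost have between half of it and none. A smaller loss without a pair, or a larger effect in those lost, would shrink the bias; a loss above 15% would increase it and also reduce power. The issue is possible bias, and it should be corrected because the remedy is simple.

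**What to change.** 1. **Section 4.4.** Separate stopping study drug from leaving the study. State that nonadherence to study drug does not by itself end data collection.
2. **Section 4.4.2.** Replace the permissive wording with a requirement to continue the headache diary and the remaining contacts to week 32, unless consent for data collection is withdrawn.
3. **Sections 3.1 and 6.** Reconcile the exclusion sentences with the visit list, so that it is clear what exclusion means at week 20. State that it does not end diary collection.
4. **Section 7.2.** Analyse these diary days under the assigned treatment. Bring in subjects with data from one period through a mixed model using all period data, at least as a sensitivity analysis, because Hills-Armitage alone cannot use them.

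The rules for when study drug is stopped are left as they are. The cost is protocol wording, diary follow-up of a few subjects, and an estimate somewhat diluted by time off drug. At 15% of 40, at most 6 subjects are involved under the plan's own dropout figure.

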4.4.2 Data Collection and Follow-up for Withdrawn Subjects

Even though a subject has withdrawn from the study, it may be important to collect some follow-up or survival data on such subjects throughout the protocol defined follow-up period. Such data is important to the integrity of the final study analysis since early withdrawal could be related to the safety profile of the study drug. If a subject withdraws consent to participate in the study, for subject safety reasons, we will make every effort to obtain permission to collect follow up information.

5 Study Drug

5.1 Description

The study drug will be a tablet containing metformin 250mg or matching-placebo. The first week of the 12 week treatment period a tablet containing metformin 250mg will be used or matching placebo, 1 tablet twice daily. After the first week, 2 tablets of metformin 250mg (total of metformin 500mg) or 2 tablets of matching placebo twice daily x 11 weeks.

5.2 Treatment Regimen

The study drug will be a tablet containing metformin 250mg or matching-placebo. The first week of the 12 week treatment period a tablet containing metformin 250mg will be used or matching –placebo, 1 tablet twice daily. After the first week, 2 tablets of metformin 250mg (total of metformin 500mg) or 2 tablets of matching placebo twice daily x 11 weeks.

This will be followed by a 4 week washout period following which the patients will be crossed over to the other arm taking either of metformin or matching placebo x 12 weeks. The first week of the 12 week treatment period a tablet containing metformin 250mg will be used or matching – placebo, 1 tablet twice daily. After the first week, 2 tablets of metformin 250mg (total of metformin 500mg) or 2 tablets of matching placebo twice daily x 11 weeks.

5.3 Method for Assigning Subjects to Treatment Groups

A statistician will create a randomized treatment allocation schedule by using a computerized random-number generator. The randomized treatment allocation schedule will be stored using the REDCap randomization module.

5.4 Preparation and Administration of Study Drug

The Mayo Clinic Pharmacy will allocate patients to the metformin-placebo sequence or the placebo-metformin sequence in a 1:1 ratio. Study drug, both metformin and matching-placebo will be prepared and distributed to subjects. Pharmacy would not be blinded.

The study drug will be stored and dispensed from the Research Pharmacy

- 

5.5 Subject Compliance Monitoring

Subject compliance with study drug regimen will be monitored during study visits.

5.6 Prior and Concomitant Therapy

A list of all current medications will be recorded for all subjects including preventive headache medications and as needed headache medications.

Subjects are allowed to use preventive headache medications during the study, however, there must have been no change within 2 months of beginning the baseline diary phase. In addition, subjects that have failed to respond to 3 or more previous preventive drug treatments will be excluded.

Subjects are allowed to use as needed headache medications for rescue treatment. However, subjects may not overuse these medications. Overuse is defined by the ICHD-3b criteria for medication overuse.

5.7 Packaging

- The study drug and any comparator agent will be compounded into capsules
- Bottles containing 336 capsules
- Study drug will NOT be shipped.
- The study drug or comparator will be labeled with drug name, Lot #, preparation date, quantity and statement
- Study drug or comparator will be labeled "Caution: Existing Drug--Limited by Federal (or United States) law to investigational use."

5.8 Masking/Blinding of Study

Patients will be allocated to the metformin-placebo sequence or the placebo-metformin sequence at random in a 1:1 ratio. The statistician will create the randomized treatment allocation schedule by using a computer random number generator. The randomized treatment allocation schedule will be concealed by storing it on the REDCap Randomization Module. The Mayo Clinic Pharmacy will allocate patients to treatments using the REDCap Randomization Module.

5.9 Receiving, Storage, Dispensing and Return

5.9.1 Receipt of Drug Supplies

The drug will be obtained or delivered from Cardinal Health or PCCA to the pharmacy at each investigative site.

Upon receipt of the of the study treatment supplies, an inventory must be performed and a drug receipt log filled out by the person accepting the shipment. It is important that the designated study staff counts and verifies that the shipment contains all the items noted in the shipping

invoice. Any discrepancies, damaged or unusable study drug in a given shipment (active drug or comparator) will be documented in the study files. The investigator must be notified immediately of any discrepancies, damaged or unusable products that are received.

5.9.2 Storage

No special handling requirements

5.9.3 Dispensing of Study Drug

The Mayo Clinic Pharmacy will allocate patients to the metformin-placebo sequence or the placebo-metformin sequence in a 1:1 ratio.

Regular study drug reconciliation will be performed to document drug assigned, drug dispensed, drug returns, and drug remaining. This reconciliation will be logged on the drug reconciliation form, and signed and dated by the study team.

5.9.4 Return or Destruction of Study Drug

At the completion of the study, there will be a final reconciliation of drug shipped, drug dispensed, drug returns, and drug remaining. This reconciliation will be logged on the drug reconciliation form, signed and dated. Any discrepancies noted will be documented and investigated, prior to return or destruction of unused study drug. Drug destroyed on site will be documented in the study files.

6 Study Procedures

After study enrollment, patients will undergo a 2-hour oral glucose tolerance test to confirm the absence of diabetes mellitus. Subjects will then keep a headache diary for 4 weeks to establish baseline characteristics, including number of migraine days per month, number of moderate to severe headache days per month, and number of days per month of acute medication use. The 4-week baseline period will be followed by 2 treatment periods of 12 weeks each, separated by a washout period of 4 weeks (total study duration, 32 weeks). For the 12-week treatment periods, subjects will receive either metformin 500mg twice daily or matching placebo twice daily.

During the first week of each 12 week treatment period, you will receive metformin 250mg twice a day or matching placebo. At week 2, the dose will be increased to metformin 500mg twice a day or matching placebo. In case of intolerable side effects, the dose will be reduced to 250mg twice a day.

Subjects will have 7 clinic visits. Routine laboratory studies and a pregnancy test will be performed at enrollment and week 20. Abnormal kidney or liver function will exclude subjects. Pregnancy will exclude subjects. General and neurologic examinations will be performed during 2 of the 7 visits. At each visit, subjects will receive medication for the period until the next visit.

7 Statistical Plan

7.1 Sample Size Determination

This will be a single-center, double-blind, randomized, placebo-controlled, crossover study. Crossover designs have been used successfully in migraine trials (Olesen, 1981). Prior migraine trials have suggested that a sample size of 34 patients has 80% power to detect a mean reduction in migraine days of 1.25 days per month, with $\alpha=0.05[Q^1]$ (σ 2.5, ρ 0.5; Hauge, 2009; Silberstein, 2004; Sorensen, 1986). We will enroll 40 subjects to account for an estimated 15% dropout rate.

